after surgery). This baseline assessment will occur at a standard postoperative clinic visit. Patients will also be asked to participate in follow-up visits at 6 and 12 months after surgery. The primary outcomes are self-reported pain, disability, and general health. Secondary and tertiary outcomes include physical activity and physical function, respectively. Additionally, use of pain medication, re-hospitalization following initial spine surgery, and surgeries following initial spine surgery will also be ascertained and compared between the two treatment groups at 6 and 12 months after surgery. A schematic of the trial design is presented below in Figure 2.

Figure 2: Trial Design

3.2. Comparators. Patients who meet the eligibility criteria and have signed an informed consent statement will be randomly assigned to one of two groups after surgery and completing the baseline assessment:

Group 1: CBPT

Group 2: Education

Randomization will provide patients a 50/50 opportunity to be in either group. The stratified randomization scheme will assign patients in randomly permuted blocks of assignments stratified by age and type of surgery (i.e., fusion or no fusion). The 4 frequency-matched strata will be as follows: (1) Age 21-59 and fusion; (2) Age 60-90 and fusion; (3) Age 21-59 and no fusion; (4) Age 60-90 and no fusion. This scheme will ensure that the two groups will be balanced by age (to minimize age effects of pain and disability) and by fusion (to minimize effects of differences in injury severity, procedural complexity, and recovery time).

The randomization plan will be prepared and administered centrally by the Coordinating Center (Vanderbilt) but will not require real time interaction with Vanderbilt staff members. Requests for randomizations will be made by the study physical therapist using a secure web-based application. An assignment will be issued only if the database shows that the patient is eligible, the consent statement has been signed, and a baseline assessment completed.

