Huntington's disease, Alzheimer's disease, Muscular Dystrophy, Stroke, Autonomic Nervous System disorders, Traumatic Brain Injury, Cerebral Palsy, and Amyotrophic Lateral Sclerosis;

6) Presence of schizophrenia or other psychotic disorder, including but not limited to Brief Psychotic disorder and Delusional disorder;

7) Patients not able to return to clinic for standard follow-up visits with surgeon due to time and travel limitation;

8) Patients having surgery under a workman's compensation claim; and

9) Unable to provide a stable address and access to a telephone indicating the inability to participate in either the telephone-based CBPT or education program.

5. Trial Protocol

5.1. Overview. The patient-related activities of the CBPT trial can be divided into the following phases:

- Phase 1: Qualitative data collection (Vanderbilt site only)
- Phase 2: Screening for eligibility;
- Phase 3: Consent and enrollment into trial prior to surgery;
- Phase 4: Baseline data collection (6 weeks after surgery);
- Phase 5: Randomization and Treatment;
- Phase 6: Post-treatment follow-up phase (6 and 12 months after surgery);

The visit and data collection schedule described below is summarized in Appendix 9.4.

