5.5. Phase 4: Baseline Data Collection. The date of surgery is the 0 time for reckoning baseline visit and all follow-up visits (i.e., all follow-up visits are scheduled at specific times measured from the date of surgery). The surgery scheduler will schedule both the surgery and a standard 6-week postoperative clinic visit for the patient. The Research Coordinator at each site will contact patients to schedule a baseline study visit prior to their standard 6-week postoperative clinic visit with the surgeon. Patients at this study visit will complete questions on work status, medication, physical therapy, expectations, and satisfaction and a battery of questionnaires to measure fear of movement, pain self-efficacy, depressive symptoms, general physical and mental health, and pain and disability outcomes. Physical function will be assessed through performance-based tests that include the Chair Stand test, 10-Meter Walk test, and

Timed Up and Go. Patients will be provided with an accelerometer to wear for 7 days following the study visit.

Study personnel conducting the baseline assessment will be unaware of the patient treatment condition. All data from the baseline self-reported assessment will be entered directly into the REDCap Data Entry System by the patient. Data from the performance based tests will be recorded on case report forms by study personnel and then transferred to the REDCap Data Entry System. Details as to the information collected during the baseline assessment is included as Appendix 9.4.

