ability to accomplish a range of activities despite pain. Participants rate how confident they are on a 7-point scale from 'not at all confident' to 'completely confident.' Scores range from 0 to 60, with a score greater than 40 indicating high pain self-efficacy (158). The PSEQ has been found to have excellent internal consistency (Cronbach's alpha > 0.90), good test-retest reliability (Pearson's r > 0.70), and construct validity through correlations with depression, anxiety, coping strategies, pain ratings, and work-related tasks in patients with chronic pain (158).

5.9 Other Outcomes. At each clinic and study visit, the treating surgeon and/or research personnel will record the type and frequency of pain medication use. Data on number of re-hospitalizations (including length of stay) and number and type of surgeries (e.g., revision spine surgery) following initial spine surgery will also be collected from medical and billing records at each site and through patient self-report.

5.10. Safety Issues. Safety issues can be divided into (i) safety concerns related to the therapeutic interventions and (ii) concerns related to patient privacy.

5.10.1. Safety Concerns Related to the Therapeutic Treatments. There are no potential adverse effects specific to the participation in cognitive and behavioral therapy and self-management interventions. There is the potential for physical discomfort (increased pain and reduced activity level) and falls due to participating in the physical performance tests. There may also be distress related to answering questions and discussing mood and pain beliefs.

5.10.2. Safety Issues Related to Patient Privacy. It is the investigator's responsibility to conduct the protocol under the current version of Declaration of Helsinki, Good Clinical Practice, and rules of local IRBs. The investigators must ensure that the patient's anonymity be maintained in their data submission to the coordinating center (Vanderbilt). Patients will only be identified by an identification code and not by their name, SSN, or hospital medical record number. Study Site Investigators will maintain a separate confidential enrollment log which matches identifying codes with the patients' names and addresses (i.e., available only to local clinic staff). All study material will be maintained in strict confidence.

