6.1. Study Aims and Hypotheses

Specific Aim 1: To determine the most important treatment outcomes to older adults undergoing lumbar spine surgery for degenerative conditions.

Hypothesis 1: The most important outcomes to older adults undergoing lumbar spine surgery will include pain, physical functioning, and general health.

Specific Aim 2: To compare whether a CBPT program or an education program are more effective in reducing disability and pain and improving general health, physical activity, and physical function following lumbar spine surgery for degenerative conditions.

Hypothesis 2: CBPT participants compared to education participants will demonstrate significantly greater improvement in disability (Oswestry Disability Index), pain (Brief Pain Inventory), general health (12-item Short Form) and physical activity (movement accelerometers) at 6 and 12 months following lumbar spine surgery and physical function as measured by standardized performance tests of strength, gait speed, and mobility (Chair Stand, 10-Meter Walk, Timed Up and Go) at 12 month follow-up.

Specific Aim 3: To determine how the CBPT treatment improves outcomes in patients following lumbar spine surgery for degenerative conditions.

Hypothesis 3: Participants reporting decreases in fear-of movement and increases in pain self-efficacy will demonstrate improvement in outcomes following the CBPT program at 6 and 12 months following lumbar spine surgery.

Specific Aim 4: To determine which sub-groups of adults are most likely to benefit from the CBPT program following lumbar spine surgery for degenerative conditions.

Hypothesis 4: CBPT participants that are 60 years or older, have a fusion procedure, and report clinically significant depressive symptoms preoperatively will demonstrate greater improvement in outcomes at 6 and 12 months following lumbar spine surgery.

6.2. Outcome Measures. The outcomes are defined above in Section 5.9. They are summarized below:

Primary Outcome Measure:

- Self-reported disability (Oswestry Disability Index)
- Self-reported pain (Brief Pain Inventory)
- Self-reported general health (SF-12)

Secondary Outcome Measure:

- Physical Activity (Movement accelerometer: total daily amount of physical activity)
- Physical Function (Chair Stand, 10-Meter Walk, Timed Up and Go)

Other Outcomes:

- Use of pain medication
- Re-hospitalization following initial spine surgery (number and length of stay)

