- Surgeries following initial spine surgery (number and type)

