7.3. Human Subjects Involvement, Characteristics, and Design. The proposed study includes community-dwelling adults who are having surgical treatment of a lumbar degenerative condition (spinal stenosis, spondylosis with or without myelopathy, and degenerative spondylolisthesis) using laminectomy with or without arthrodesis (i.e., fusion) procedures. Eligible and consenting participants will return for a 6 week postoperative clinic baseline visit. At this postoperative visit, all participants will complete a baseline assessment and will then be randomized to one of the 2 study groups (CBPT vs. education). Based on preliminary data, the study population will be on average 59 years of age, 59% female, and 84% White. All human subjects training and assessment will require approval from the Vanderbilt and Johns Hopkins Institutional Review Board (IRB), and all human subjects' involvement will utilize informed consent documentation.

7.4. Sources of Materials. All materials will be collected and recorded for research purposes. The socio-demographic, clinical, and outcomes information collected during this investigation will be obtained from multiple sources, including subjects directly, medical records, and hospital databases. These data will be entered directly into REDCap (a secure, web-based application) when possible or recorded on case report forms and then transferred to REDCap when necessary (e.g., performance-based physical function test results). All data will be secured by password-only access for the purpose of confidentiality. The surgery and clinic notes will also be used to collect data. Outcomes data will be derived from questionnaires completed both in the clinic and at home and activity monitors, and through interactions between the patient and research personnel during physical performance tests. Study personnel collecting the outcome data will be unaware of the patient treatment condition.

7.5. Potential Risks. The risk to human subjects of participation in this study is minimal due to the nature of this behavioral treatment. The possibility exists that a subject may experience a degree of emotional discomfort related to learning about and managing elevated fear of movement beliefs and

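### Re-hospitalisation and further surgery are counted from the index operation, but arms are assigned about 6 weeks later and no rule sets aside the events in between (minor)

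*Combined protocol and SAP*

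**What the plan says.** **Where counting starts.** Section 3.1 says that "surgeries following initial spine surgery will also be ascertained and compared between the two treatment groups at 6 and 12 months after surgery"; its sentence names re-hospitalisation on the same terms. Section 6.2 lists the two event outcomes as "Re-hospitalization following initial spine surgery (number and length of stay" and "Surgeries following initial spine surgery (number and type". Section 5.9 gives the source: data on events "following initial spine surgery will also be collected from medical and billing records at each site and through patient self-report". Section 5.5 fixes the clock: "The date of surgery is the 0 time for reckoning baseline visit and all follow-up visits".

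**When arms exist.** Section 5.1 places the baseline in "Phase 4: Baseline data collection (6 weeks after surgery". Section 7.3 says that at this visit "all participants will complete a baseline assessment and will then be randomized to one of the 2 study groups". Section 5.6 issues an assignment only once the postoperative baseline assessment is complete, and treatment sessions follow (5.6.1).

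**What bears on the gap.** Appendix 9.4 marks re-hospitalisation and additional surgery at baseline, 6 months and 12 months. Section 5.7 has patients asked at follow-up about intervening events, without a look-back date. Section 6.3.2 plans to adjust for the baseline value of each outcome variable. No eligibility criterion in 4.2 or 4.3 removes a patient who is readmitted or reoperated on before the baseline visit.

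**The concern.** A readmission in week 2 precedes an assignment made in week 6, so it cannot be an effect of CBPT or of education. With counting from the index operation and no exclusion rule, it can still enter the between-arm comparison.

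The resulting count is hard to interpret in two ways. It is not purely a treatment outcome, because it contains events from before assignment. It is not a full postoperative event rate either, because a patient whose early complication prevents the baseline visit never enters an arm. At stake are the precision of two descriptive comparisons and, if a ratio is reported, its size.

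**Working it through.** **Figures in the plan.** The plan states no event rate, event timing, effect measure or power for these two outcomes, so there is nothing of its own to reproduce here. The trial's size (260 consented, 221 retained, 260 × 0.85 = 221; target 110 per arm in 6.5) does not depend on them.

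**Step 1: share of each window before randomisation.** Surgery is week 0 and the baseline is at 6 weeks.
- 6-month window: 6/26 = 0.231
- 12-month window: 6/52 = 0.115

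**Step 2: effect on a difference and on a ratio.** Let *a* be the mean early count, equal in both arms in expectation because assignment comes later. Let *b* be the mean later count under education and *rb* under CBPT.
- Difference: (a + rb) − (a + b) = (r − 1)b. The early events cancel.
- Ratio: (a + rb)/(a + b) = f + (1 − f)r, where f = a/(a + b).

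**Step 3: ratio, with r = 0.70 assumed.**
- Even spread, 12 months (f = 6/52): 0.115 + 0.885 × 0.70 = 0.735
- Even spread, 6 months (f = 6/26): 0.231 + 0.769 × 0.70 = 0.77
- f = 0.30: 0.30 + 0.70 × 0.70 = 0.79
- f = 0.50: 0.50 + 0.50 × 0.70 = 0.85

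**Step 4: precision.** This is an illustration with 110 per arm, two-sided 0.05, an assumed 12-month risk of 20% under education and an assumed true post-randomisation risk ratio of 0.5. Early and later risks are simply added, so a patient is not counted in both. With f = 0.115:
- From surgery: 20.00% against 20% × (0.115 + 0.885 × 0.5) = 11.15%; difference 8.85 points
- From randomisation: 20% × 0.885 = 17.70% against 8.85%; difference 8.85 points

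The difference is the same. Only the variance, and so the power, changes.

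| Early share f | Early events among 220 | Ratio from surgery | Power, from surgery | Power, from randomisation |
|---|---|---|---|---|
| 11.5% | 5.1 | 0.56 | 44% | 49% |
| 25% | 11.0 | 0.63 | 33% | 42% |
| 40% | 17.6 | 0.70 | 22% | 34% |

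If the assumed 12-month risk runs from 10% to 24%, power runs from 12% to 52% counting from surgery and from 19% to 58% counting from randomisation. Section 2.1 cites reoperation in 20% to 24% of patients but gives no time span, so it only loosely supports the upper end.

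**The case against.** **The wording may only separate repeat events from the index admission.** Appendix 9.4 has a baseline column for both items, section 5.7 speaks of intervening events, and the comparison is made at 6 and 12 months. That fits interval records in which weeks 0 to 6 stay in the baseline column. This reading is possible, so a reader should not infer that the plan expressly assigns a week-2 readmission to an arm. What stands against it is that no sentence says the counts are per interval, and recording early events separately does not exclude them from the outcome.

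**Baseline adjustment.** If section 6.3.2 covers these outcomes, a linear model with the early count as a covariate would recover much of the lost precision. But that section does not name them, and adjustment would not alter the reported numbers, lengths of stay or types of surgery.

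**Randomisation balances early events.** This stands in full. A reader might infer bias toward one arm, or that any real difference shrinks toward zero. Neither follows: the expected difference in counts is unchanged (Step 2), and chance imbalance in early events is ordinary sampling error that the test allows for. Only a ratio is diluted, and the plan names no ratio measure for these outcomes. The models it writes out in 6.3.2, 6.3.4 and 6.5 are linear models of change.

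**Importance.** A reader might take these as the trial's only hard clinical events. Section 5.13.2 also monitors adverse events, some of them as secondary outcomes, and serious events include death. The two items belong to no hypothesis and have no stated power.

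**Conclusion.** The concern holds as a gap in definition. The stated starting point for both outcomes is the index operation, arms exist only from about week 6, and nothing keeps the intervening events out of the comparison. The gap covers 23% of the 6-month window and 11.5% of the 12-month window.

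The consequence is added variance and, if a ratio is used, movement toward 1. Under even spread, an assumed true ratio of 0.70 would read 0.735 at 12 months and 0.77 at 6 months. Larger dilution is easy to compute: a 30% reduction would read as 15% if half of the 12-month events fell before randomisation. The documents do not support presenting that as the expected effect, because they give neither event timing nor a ratio scale. The power figures likewise rest on assumed risks, effect and early shares. Across the values tried, counting from randomisation was more precise every time, despite fewer events.

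Severity is minor. No primary or secondary conclusion, and no figure in the plan, changes.

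**What to change.** - In sections 3.1, 5.9 and 6.2, define both outcomes as events with onset after the date of randomisation, through 6 and through 12 months after surgery.
- Record the date of each readmission and operation. Section 5.9 lists number, length of stay and type but not dates; the medical and billing records already being searched are the natural source.
- State the look-back for the follow-up questions in section 5.7, for example since randomisation at 6 months and since the previous visit at 12 months.
- Report events between surgery and randomisation by arm, as baseline characteristics only.

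The cost is a wording change, one date field per event, and slightly fewer counted events. No new visit or procedure is needed, and the sample size is unaffected.

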5.2. Phase 1: Qualitative Data Collection (Vanderbilt only)

5.2.1. Patient Interviews. Twenty interviews will be conducted at Vanderbilt to identify patient-centered outcomes for the randomized controlled trial. However, data collection will occur until redundancy or saturation is reached (i.e., no additional information is obtained from the last informants). Interview participants will be recruited through a stratified purposeful sampling approach from a current cohort of 80 adults who have been enrolled into a NIH-funded pilot trial comparing the CBPT and education programs. This purposeful sample will be stratified by responders (i.e., reduction in disability of 12.8 points or greater as measured by the Oswestry Disability Index) or non-responders (i.e., reduction < 12.8 points) at 12 months following surgery. Research personnel will contact eligible individuals by mail and then phone to determine interest in participation and verbal and written consent will be obtained.

5.2.2. Focus Groups. After the interviews, focus groups will be conducted to: 1) identify any outcomes that might have been missed by the interviews; 2) review existing measurement scales used to capture all identified outcomes; 3) generate discussion on how measurement scales might be improved to better capture patients' actual experiences with these outcomes over time and across contexts (e.g., work, family, recreation); and 4) to review models of patient surgical outcomes developed from the interviews. Four focus groups are planned, with 6 to 8 participants in each. Groups will be comprised of patients that were not involved in the interview process and recruitment will occur through the stratified purposeful sampling approach described above. 2 hours will be allotted for each group. Groups will be led by [name] (co-investigator) and an experienced moderator from the Qualitative Research Core

at Vanderbilt University. Focus group participants will be asked to read and sign informed consent forms at the start of the session. Groups will include a spontaneous reporting of symptoms and health concerns and how patients managed symptoms. Then codes and categories (i.e., outcomes) will be presented that were identified through the interviews. Measures will also be presented that reflect these outcomes to answer the research question – “*Do outcome measures commonly used in surgical spine trials adequately reflect what is most important to patients?*”

5.2.3. Pilot Testing and Cognitive Interviews. The final outcome measures/items will be piloted via mail or email with 25 patients who have participated in the interviews or focus groups. Ten additional patients will be recruited for in-person cognitive interviews (i.e., talk out loud as they complete the measurement tool). The cognitive interviews will assess the following for the outcome scales/items: 1) comprehension; 2) process by which the respondent retrieves relevant information from memory; 3) decision process to answer each item; and 4) response process.

5.3. Phase 2: Screening for Eligibility. Patients will be screened for eligibility in each center by the local research coordinator in close coordination with the surgeon co-investigators. Screening through the medical record will occur prior to surgery and a scheduled preoperative clinic visit. Additional screening will occur either during the preoperative clinic visit or after by the study coordinator through a list of screening questions. All potentially eligible patients will be entered into REDCap, a study number assigned, and eligibility criteria confirmed. The Coordinating Center (Vanderbilt) will be available to adjudicate eligibility.

5.4. Phase 3: Consent and Enrollment. Eligibility will be confirmed with the treating surgeon and through a list of screening questions for the patient. Patients will then be approached for their consent to participate in the randomized controlled trial following their preoperative clinic visit. The study coordinator will perform the consent process using a scripted dialogue and materials developed for the CBPT study. A power point presentation will also be made available for use by the research team to describe the study and what it means to participate in the study.

Once consented into the randomized trial, patients will complete a preoperative questionnaire. This assessment will gather data on patient demographic and injury characteristics, medical and social history, expectations of surgery, fear of movement, pain self-efficacy, affect, depressive symptoms, and preoperative levels of pain, disability, and general physical and mental health. Patients will also be asked to complete a battery of physical performance tests to assess strength, mobility, and gait speed.

5.5. Phase 4: Baseline Data Collection. The date of surgery is the 0 time for reckoning baseline visit and all follow-up visits (i.e., all follow-up visits are scheduled at specific times measured from the date of surgery). The surgery scheduler will schedule both the surgery and a standard 6-week postoperative clinic visit for the patient. The Research Coordinator at each site will contact patients to schedule a baseline study visit prior to their standard 6-week postoperative clinic visit with the surgeon. Patients at this study visit will complete questions on work status, medication, physical therapy, expectations, and satisfaction and a battery of questionnaires to measure fear of movement, pain self-efficacy, depressive symptoms, general physical and mental health, and pain and disability outcomes. Physical function will be assessed through performance-based tests that include the Chair Stand test, 10-Meter Walk test, and

Timed Up and Go. Patients will be provided with an accelerometer to wear for 7 days following the study visit.

Study personnel conducting the baseline assessment will be unaware of the patient treatment condition. All data from the baseline self-reported assessment will be entered directly into the REDCap Data Entry System by the patient. Data from the performance based tests will be recorded on case report forms by study personnel and then transferred to the REDCap Data Entry System. Details as to the information collected during the baseline assessment is included as Appendix 9.4.

5.5.1. Accelerometer Data. Each accelerometer will be initialized at the Coordinating Center (Vanderbilt) to record three-dimensional accelerations raw signal at 40 Hz. However, detailed instructions on how to wear and care for the accelerometer will be provided by the Study Coordinator at each local site during the baseline visit. Patients will be asked to wear the accelerometer secured at the right hip with a waist belt for seven consecutive days excluding night rest (sleep). All patients will also be given a stamped, self-addressed envelope to return the accelerometer to the Coordinating Center (Vanderbilt) after wearing for seven days. Research personnel at Vanderbilt will download the data using ActiLife v6.4 software. If wear interval data are not available for at least 4 days (with each day being at least 10 hours), the Research Coordinator at the Coordinating Center (Vanderbilt) will contact the patient by phone and ask them to wear the accelerometer for another 7 days. The accelerometer will then be mailed from the coordinating center (Vanderbilt) to the patient along with a self-addressed stamped envelope to return after wearing for seven days.

5.6. Phase 5: Randomization and Treatment. Once the patient has been consented, undergone surgery for a lumbar degenerative condition, and completed the baseline assessment, the Research Coordinator at each site will update the REDCap Data Management System and the patient will be randomized electronically. To ensure that the number of subjects is about the same in the two arms of the study for each clinical site, the randomization scheme will assign patients in a 1:1 ratio in randomly permuted blocks of assignments stratified by age and type of surgery (i.e.; fusion or no fusion). Block size will be determined randomly with the patient as the unit of randomization.

The randomization plan will be prepared by the study's biostatistician and administered centrally by the Coordinating Center (Vanderbilt), but will not require real time interaction with Vanderbilt staff members. Requests for randomization will be made by the study therapist using a secure web-based application. An assignment will be issued only if the database shows that the patient is eligible, the consent statement has been signed, and a baseline postoperative assessment completed. Enrollment will be documented in the patient's chart according to center protocol.

5.6.1. Treatment. Once patients have completed the baseline assessment with the Research Coordinator and received the movement accelerometer, the study physical therapist will call the patient to schedule the first treatment session. Patients will complete 6 sessions over the phone. Sessions will be scheduled on a weekly basis.

5.7. Phase 6: Post-treatment Follow-up Phase (6 and 12 months after surgery). The randomization computer program will generate a personalized appointment schedule for the patient; this schedule will

indicate the ideal date for each follow-up visit, as well as the time window around the ideal date during which the follow-up visit may be done.

Patients will have follow-up visits at 6 and 12 months after surgery. Each visit will have an interval of time surrounding the ideal date for the visit during which the visit may be done and the data included in the trial database. The ideal date for a visit is the exact anniversary from surgery. Visit windows (+/- 2 weeks for all visits) will be constructed to be contiguous, so that at any point in time, some visit window is open, subject to a check on the minimum separation required between consecutive visits. Patients at the study follow-up visits will complete the same questions and battery of questionnaires as the baseline assessment and wear an accelerometer for 7 days. Patients will also be asked questions on intervening events such as re-hospitalization and surgery. At the 12-month follow-up, patients will return for an on-site visit and complete the performance-based tests.

Study personnel conducting the follow-up assessment will be unaware of the patient treatment condition. All data from the follow-up self-reported assessment will be entered directly into the REDCap Data Entry System by the patient or on case-report forms. Data from the performance based tests will be recorded on case report forms by study personnel and then transferred to the REDCap Data Entry System. The types of specific data to be collected at each of the follow-up visits are included as Appendix 9.4.

5.7.1. Accelerometer Data. See section 5.5.1 for procedures with regard to accelerometers.

5.8. Outcomes. All outcomes will be assessed using widely used, standardized measures. They are described below.

5.8.1. Primary Outcomes. The Brief Pain Inventory (BPI) (123) will assess pain intensity. The 4-item pain intensity subscale assesses current, worst, least, and average pain. The subscale uses a numerical rating scale with 0 representing 'no pain or does not interfere' and 10 representing 'pain as bad as you can imagine or completely interferes.' Scores greater than or equal to 5 indicate moderate to severe pain intensity and interference. The BPI has proven both reliable (Cronbach's alpha > 0.80) and valid (highly correlated with well-validated generic measures of pain and general health and condition specific disability) in both surgical patients and patients with chronic low back pain (124-126). The minimum clinically important difference (MCID) for pain has been found to range from 1.2 to 2.1 points in patients following lumbar spine surgery (127). The 10-item Oswestry Disability Index (ODI) (128) is a standard measure of condition specific disability that assesses the impact of lumbar spinal disorders on daily living, with questions about pain intensity, lifting, sitting, standing, walking, sleeping, hygiene, traveling, social life, and sex life. Ratings for each item are from 0 (high functioning) to 5 (low functioning). Total scores are divided by the total possible score and multiplied by 100 to create a percentage of disability. The ODI has demonstrated strong test-retest reliability (Pearson's $r > 0.80$) and validity, and good internal consistency (Cronbach's alpha > 0.70) in both surgical spine patients and patients with chronic low back pain (129-130). The MCID has been found to range from 8.2 to 12.8 points in patients following lumbar spine surgery (127,131). General physical and mental health will be measured with the physical and mental composite scales of the SF-12 (132). The physical component scale (PCS) assesses the four subdomains of physical functioning, role-physical, bodily pain, and general health and the mental component scale (MCS) assesses the 4 subdomains of vitality, social

functioning, role-emotional, and mental health. Total subscale scores range from 0 to 100, with 100 indicating the highest level of health. The PCS and MCS of the SF-12 have demonstrated responsiveness, good test–retest reliability, good internal consistency, and validity with correlations greater than 0.90 with the SF-36 in generalized and various patient populations (132-134). The minimal clinically significant change for the PCS and MCS has been estimated at 10% (134).

5.8.2. Secondary Outcome. Physical activity will be measured objectively using a commercially available movement accelerometer (ActiGraph GT3X+), a small triaxial accelerometer (46 mm × 33 mm × 15 mm) that weighs approximately 19 grams (135). The water resistant device assesses acceleration in three individual orthogonal planes using a vertical axis, horizontal axis and a perpendicular axis. Accelerometers are used in physical activity monitoring because of their small size, low cost, convenience, the ability to record data for several days (136), and ability to assess multiple dimensions of physical activity (e.g., total activity, time spent in different levels of intensity and predicted energy expenditure) (137-139). Accelerometers have proven valid with moderate correlations with the criterion method of doubly labeled water for total and active energy expenditure in young and older adults (140,141). For the purpose of this study, the monitor will be initialized to record three-dimensional accelerations raw signal at 40 Hz. Physical activity will be assessed using total volume of physical activity, expressed as the mean counts per minute over the duration of accelerometer monitoring. In addition, percentage of time spent in commonly used domains of physical activity intensity (sedentary, light, moderate, and vigorous) will be considered.

Chair Stand test from the Short Physical Performance Battery (SPPB) from the Established Populations for the Epidemiologic Study of the Elderly studies will be used to assess strength (142). The Chair Stand test has demonstrated good to excellent test-retest reliability, good internal consistency (Cronbach's alpha > 0.70), and predictive validity in analyses showing risk for mortality and disability (143,144). The 10-Meter Walk (146) test will measure self-selected walking speed. Ambulatory support devices may include canes, crutches, or walkers and will be recorded. The time it takes for subjects to complete the task is measured with a stop watch and recorded as meters per second (m/sec). Excellent inter-rater and intra-rater reliability (ICC > .90) and good test-retest reliability for self-paced timed walking speed tests using a stopwatch have been reported (146). Validity for walking speed tests has been determined by significant correlations with self-report measures of function and mortality in older adults (146,147). The MCID for the 10-meter walk test at a comfortable pace has been estimated to be 0.16 meter/second and a meaningful change in older adults has been documented at 0.10 meter/second (148). The Timed Up and Go (TUG) test will be used to assess functional mobility (149). Time less than 10 seconds indicates functional independence and more than 30 seconds demonstrates functional dependence. The TUG has been shown to have excellent test-retest reliability (149,150) and be a valid and responsive performance measure in older individuals (151). The MCID for the TUG has been reported as a reduction in time ranging from 1.2 to 2.3 seconds in older adults with pain (152).

5.8.3. Intermediary Outcomes. The Tampa Scale for Kinesiophobia (TSK) (153) will be used to measure fear of movement. Participants are asked to rate each item on a 4-point Likert scale with scoring alternatives ranging from 'strongly disagree' to 'strongly agree.' The MCID for the TSK has been reported to be 4 points in patients with back pain (154). The TSK has been found to have good internal consistency (Cronbach's alpha > 0.70) and test-retest reliability (Pearson's r > 0.70) in surgical patients and patients with various musculoskeletal conditions (155,156). The 10-item Pain Self-Efficacy Questionnaire (PSEQ) (157) will measure the strength and generality of a person's belief in his/her

ability to accomplish a range of activities despite pain. Participants rate how confident they are on a 7-point scale from 'not at all confident' to 'completely confident.' Scores range from 0 to 60, with a score greater than 40 indicating high pain self-efficacy (158). The PSEQ has been found to have excellent internal consistency (Cronbach's alpha > 0.90), good test-retest reliability (Pearson's r > 0.70), and construct validity through correlations with depression, anxiety, coping strategies, pain ratings, and work-related tasks in patients with chronic pain (158).

5.9 Other Outcomes. At each clinic and study visit, the treating surgeon and/or research personnel will record the type and frequency of pain medication use. Data on number of re-hospitalizations (including length of stay) and number and type of surgeries (e.g., revision spine surgery) following initial spine surgery will also be collected from medical and billing records at each site and through patient self-report.

5.10. Safety Issues. Safety issues can be divided into (i) safety concerns related to the therapeutic interventions and (ii) concerns related to patient privacy.

5.10.1. Safety Concerns Related to the Therapeutic Treatments. There are no potential adverse effects specific to the participation in cognitive and behavioral therapy and self-management interventions. There is the potential for physical discomfort (increased pain and reduced activity level) and falls due to participating in the physical performance tests. There may also be distress related to answering questions and discussing mood and pain beliefs.

5.10.2. Safety Issues Related to Patient Privacy. It is the investigator's responsibility to conduct the protocol under the current version of Declaration of Helsinki, Good Clinical Practice, and rules of local IRBs. The investigators must ensure that the patient's anonymity be maintained in their data submission to the coordinating center (Vanderbilt). Patients will only be identified by an identification code and not by their name, SSN, or hospital medical record number. Study Site Investigators will maintain a separate confidential enrollment log which matches identifying codes with the patients' names and addresses (i.e., available only to local clinic staff). All study material will be maintained in strict confidence.

